**The following elements will be assessed with a blood draw and after obtaining informed consent.**

1. Absolute Neutrophil count (ANC)  $\geq 750/\text{mm}^3$
2. Hemoglobin  $\geq 10.0$  g/dL for women and Hemoglobin  $\geq 11.0$  g/dl for men
3. Platelet count  $\geq 75,000/\text{mm}^3$
4. Estimated Glomerular Filtration Rate (eGFR)  $>60$  mL/min, eGFR will be calculated using the Chronic Kidney Disease Epidemiology Collaboration (CKD-EPI) equation

5. Confirmed serum glutamate pyruvate transaminase (SGPT)/serum glutamate oxaloacetate transferase (SGOT)  $\leq 3$  times the upper limit of normal (ULN)
6. INR  $\leq$  the ULN for the assay
7. Negative urine pregnancy test of child bearing potential at randomization
8. No evidence of active hepatitis B or hepatitis C (active hepatitis B will be defined as a positive hepatitis B surface antigen present on a single determination, whereas a positive result on hepatitis C RNA will be considered as evidence of active hepatitis C)

All routine laboratory testing used to determine safety will be completed within the 70 days prior to randomization.

### **Participant Exclusion Criteria**

1. Known bleeding diathesis (for example a diagnosis of hemophilia or Von Willebrand disease)
2. Active drug use or alcohol abuse/dependence, which in the opinion of the investigators will interfere with the patient's ability to participate in the study
3. Serious illness requiring systemic treatment and/or hospitalization within 30 days of screening into the study
4. Evidence of active opportunistic infections or neoplasms (excluding cutaneous basal cell carcinoma and squamous cell carcinoma) in the 6 months prior to randomization
5. History of inflammatory bowel disease (Crohn's Disease, ulcerative colitis)
6. Positive urine pregnancy test at screening (of child bearing potential).
7. Breastfeeding
8. Current imprisonment
9. Concurrent immunomodulatory agents, including systemic corticosteroids in the 12 weeks prior to randomization. Topical, nasal or inhaled corticosteroid use is allowed
10. Concomitant use of probiotics except yogurt
11. Chronic antibiotic use such as tetracyclines for acne
12. Vaccinations within 6 weeks of randomization
13. Concomitant use of anticoagulants (other than aspirin and NSAIDs) is an exclusion criterion for subjects opting in for the colonoscopy. Aspirin and NSAIDs will be discontinued per each institutions requirement before the procedure.
- 14 Child-Pugh Class C disease
- 15 A prior history of *Clostridium difficile* colitis
- 16 Any condition that precludes the safe administration of conscious sedation for endoscopy (such as decompensated lung or heart disease) will not be able to participate in the colonoscopy aspect of the protocol

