In general, the use of antibiotics has been associated with emergence of *Clostridium difficile* diarrhea. While no cases of *C. difficile* were reported in a study of IBS subjects randomized to receive a 2 week course of rifaximin, [92] three cases of *C.difficile* colitis were observed (2 in the rifaximin arm and 1 in the placebo arm) in the randomized placebo-controlled trial that examined the use of rifaximin in subjects with HE.[19] In this study, subjects who developed *C.difficile* while receiving rifaximin reported other concurrent risk factors including multiple recent hospitalizations, receipt of proton pump inhibitors, and other antibiotics[19]. Rates of *C.difficile* colitis in this study were similar between the rifaximin and placebo arm. While it is possible that rifaximin use resulted in *C. difficile* colitis in these two study participants, it is interesting to note that rifaximin has *in vitro* activity against *C. difficile*,[94] and has shown utility in refractory *C. difficile* infection in combination with vancomycin, and as sequential therapy [95-97].

Adverse effects are limited and mostly confined to the gastrointestinal tract. The following side effects have been observed in over 2% of subjects treated with rifaximin for travelers' diarrhea: flatulence, headache, abdominal pain, rectal tenesmus, defecation urgency, nausea, constipation, pyrexia, and vomiting. It is important to note that the dose and duration of rifaximin used for the treatment of travelers' diarrhea is lower and shorter than that being used in this study. Hypersensitivity to rifaximin has been rarely observed in post-marketing experience,[98] and is characterized by exfoliative dermatitis, rash, angioneurotic edema, urticaria, flushing; pruritus and anaphylaxis have been reported. Rifaximin is considered a pregnancy category C agent, and its excretion in breast milk is unknown.

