### **3 STUDY DESIGN**

#### **3.1 Description**

The study will be conducted as a randomized, double-blind, placebo-controlled trial and utilize a case cross-over design. In such a study design each subject serves as his or her own control. Such a study design avoids issues related to the inter-individual variability associated with response to treatment. Both the primary and secondary objectives will be evaluated in ART-treated subjects who have suppressed viremia as measured by standard assays. Subjects will be initially randomized to receive a 4 week course of rifaximin or placebo. Upon completion of a 4 week course of rifaximin or placebo they will undergo a 4-6 week washout period and cross over treatment assignments to complete a 4 week course of either rifaximin or placebo. The duration of 4 weeks was chosen as studies in cirrhotic patients suggest that both plasma endotoxin levels and biomarkers of inflammation show statistically significant declines, ~50%, after 28 days of rifaximin therapy [100-101]. Both these studies also used a dosage of 1200 mg. In this study, we will be using a 1100 mg dose as the drug is approved at a 550 mg dose. A 4-6 week washout period was chosen as studies in subjects with ulcerative colitis suggest that the concentration of intestinal microbial groups return to initial values after approximately a 4 week wash-out following rifaximin therapy [101-102].

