#### **4.7 Prohibited Medications and Procedures**

Treatment with immunomodulating agents including systemic steroids in the 3 months prior to screening will not be permitted as these drugs have the potential to affect the primary outcome of the study. Subjects on topical steroids will not be excluded. Concurrent statin use will be permitted if subjects have been receiving stable doses of statins for 6 or more months. The use of concurrent antibiotics/oral steroids will not be permitted while on study drug. If a subject needs to initiate antibiotic/oral steroid therapy while he/she is on the study drug, the patient will discontinue the study drug, complete the course of antibiotics/oral steroids, undergo a 4 week washout and will re-initiate the study drug starting from Day 0 of the treatment phase. Subjects initiating antibiotics/oral steroids during the screening or washout phases of the study will have these phases extended by 4 weeks after completion of the antibiotic/oral steroid course. Routine vaccinations (i.e., influenza) may be administered during the screening process or washout phase. Subjects receiving routine vaccinations during the washout phase will have their washout extended to 6 weeks.

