### **5 STUDY SCHEDULE**

#### **5.1 Screening Visits 1 and 2**

After signing the study informed consent, subjects will undergo 2 screening visits.

At the first screening visit subjects will undergo HIV testing (screening/confirmation if prior documentation of HIV status is unavailable)

Subjects found to be eligible for the study after the first screening visit will undergo the following procedures during the second screening visit:

- Complete medical history and physical examination
- Blood draw for
  - Immunophenotyping to include a CD4+ count and cellular markers of activation (including CD38+ and HLA-DR co-expression on both CD4+ and CD8+ cells)
  - Markers of bacterial translocation (including LPS, bacterial 16SrDNA or bacterial RNA and sCD14)
  - Liver function tests (including bilirubin, alkaline phosphatase (SAP), AST and ALT)
  - Renal function tests (including blood urea nitrogen (BUN), creatinine, electrolytes)
  - Complete blood count with differential (including platelets)
  - Coagulation parameters (including prothrombin time (PT) and international normalized ratio [INR])
  - Hepatitis B panel (including hepatitis B surface antigen)
  - Hepatitis C RNA assay
  - Single copy assay

Screening visits 1 and 2 must be separated by 48 hours and be no more than 65 days apart.

Screening visit 2 must be completed prior to randomization. Standard safety laboratory testing (blood counts, renal and liver function tests, coagulation studies, Hepatitis B and C panels) will be completed at the enrolling site. To minimize variability, all remaining laboratory testing will be done centrally at the NIH laboratory [Leidos Biomedical Research, Inc.].

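### A short antibiotic course completed before Screen 1, or already running then, triggers no antibiotic-free interval before Day 0, although the plan applies 4 weeks to courses begun later

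*Combined protocol and SAP*

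**What the plan says.** **Entry criteria (Participant Exclusion Criteria, under 3.4).** Item 11 reads "Chronic antibiotic use such as tetracyclines for acne". Item 3 also catches some antibiotic use, through "Serious illness requiring systemic treatment and/or hospitalization within 30 days of screening into the study". No other criterion concerns antibiotics. The same list gives look-back periods for other exposures. Item 9 covers "Concurrent immunomodulatory agents, including systemic corticosteroids in the 12 weeks prior to randomization", item 12 covers vaccination in the 6 weeks before randomization, and the inclusion criteria ask for 6 months of stable dosing if a statin is taken.

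**On-study rules (4.7).** "Subjects initiating antibiotics/oral steroids during the screening or washout phases of the study will have these phases extended by 4 weeks", counted from the end of the course. Also, "The use of concurrent antibiotics/oral steroids will not be permitted while on study drug". If a course has to start on study drug, the subject stops, finishes the course, washes out for 4 weeks and restarts the phase. Section 5.5 repeats the rule for the washout.

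**Rationale for 4 weeks (3.1).** The washout is justified by a report in ulcerative colitis that the "concentration of intestinal microbial groups return to initial values after approximately a 4 week wash-out following rifaximin therapy".

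**Timing (5.1, 5.2).** "Screening visits 1 and 2 must be separated by 48 hours and be no more than 65 days apart". Screen 2 must precede randomization, but no minimum gap is given. Study product starts the day after randomization.

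**The concern.** The plan treats 4 antibiotic-free weeks as the condition for a clean start in three situations: courses begun in screening, in washout and on study drug. It leaves out a fourth, the course begun before screening. Because the trigger in 4.7 is initiation, the same prescription delays Day 0 until 4 weeks after its end if it starts the day after Screen 1, and does not delay Day 0 at all if it finishes the day before. A course that straddles Screen 1 also falls outside the wording. No reason is given for the distinction, and steroids, which 4.7 pairs with antibiotics in its on-study rules, do have a look-back.

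The intervention is itself an antibiotic acting on gut flora. A subject admitted this way may have Phase 1 Day 0 sCD14 and stool measured while flora is recovering from something else, whereas Phase 2 Day 0 is protected by at least 4 weeks. The Phase 1 change from Day 0 would then mix that recovery with the effect of the assigned product. The analysis plan does not pick this up: the sensitivity analysis in 12.3 removes only patients given steroids or another antibiotic during a treatment period. Section 4.6 records medication taken during participation, so a course already finished may not be recorded at all.

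**Working it through.** **1. The plan's own power figure.** Inputs from 12.2: SD 0.45, correlation 0.71, difference 0.20 (all sCD14 in pg/mL × 10⁶), 40 evaluable, alpha 0.05, two-sided by 12.3.

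- SD of the paired difference = 0.45 × √(2 × (1 − 0.71)) = 0.343.
- Noncentrality = 0.20 / (0.343 / √40) = 3.69. With 39 degrees of freedom the power is 94.9%.

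The stated 95% reproduces. None of these inputs depends on the antibiotic criterion, so closing the gap changes neither sample size nor power.

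**2. Which courses are covered before Phase 1.**

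| Course | Rule that applies | Interval before Day 0 |
|---|---|---|
| Chronic use | Item 11 | Excluded |
| For serious illness, within 30 days of screening | Item 3 | Excluded |
| Started during screening | 4.7 | 4 weeks after the course ends |
| Short, non-serious, ended before Screen 1 | None | None |
| Short, non-serious, begun before Screen 1 and still running | Only the bar on use while on study drug | None |

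**3. Shortest antibiotic-free time the wording permits.**

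- Completed course: last dose the day before Screen 1 (1 day), plus 48 hours to Screen 2 (2 days), plus no stated minimum to randomization (0 days), gives 3 days at Day 0 and 4 at first dose.
- Running course: it must stop before study product starts, which is the day after Day 0. The last dose can therefore fall on Day 0, leaving 0 days at baseline.

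| Phase 1 visit | Completed course | Running course |
|---|---|---|
| Day 0 | 3 days | 0 days |
| Day 7 | 10 days | 7 days |
| Day 14 | 17 days | 14 days |
| Day 28 | 31 days (28 to 34 with the ±3-day window) | 28 days (25 to 31) |

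Day 0, Day 7 and Day 14 fall short of 28 days. Day 28 is at or about 28 days.

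**4. Bias or noise in the difference of differences.** Orient it as the change on rifaximin minus the change on placebo, and let an affected subject's Phase 1 Day 0 value be shifted by *b*. If that subject takes rifaximin first, the difference of differences moves by −*b*; if placebo first, by +*b*. The mean over *n* subjects moves by

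*b* × (affected placebo-first − affected rifaximin-first) / *n*.

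With 22 subjects randomized to each sequence, the bracket has expectation zero. For scale only, assume *b* = 0.20, the whole planned difference, and *n* = 40. Each subject of net imbalance then moves the mean by 0.20 / 40 = 0.005, or 2.5% of 0.20.

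**The case against.** The strongest reply is that the tested primary endpoint compares Day 28 with Day 28 (12.1, 12.3), and the plan's own recovery time has roughly elapsed by Phase 1 Day 28. The difference of differences is an additional examination and the stool comparison is exploratory. This stands, and it sets the low severity.

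Second, randomization spreads such subjects over both sequences, so an additive disturbance cancels in expectation. This also stands, with one reservation: cancellation assumes the same shift whichever product follows. If rifaximin acts differently on flora already reduced, the cancellation is not exact. The documents give nothing from which to size that.

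Third, the 3-day path is a literal minimum. Screen 2 is for subjects found eligible after Screen 1, which needs a viral RNA result, and several Screen 2 results are themselves entry criteria. Real intervals will usually be longer. The documents give no turnaround times, however, and nothing in them brings the interval to 28 days.

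Fourth, the 4-week recovery figure concerns rifaximin in ulcerative colitis. Carrying it over to other antibiotics is inference, although 4.7 makes the same extension for courses started on study.

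A reader might also infer a safety problem, because 1.1 lists "multiple recent hospitalizations, receipt of proton pump inhibitors, and other antibiotics" as concurrent risk factors in subjects who developed *C. difficile* on rifaximin. The documents do not support that step. The account concerns two patients with hepatic encephalopathy and several risk factors, and says nothing about a short course finished before entry. Concurrent antibiotics on study drug are barred, and prior *C. difficile* colitis is an exclusion.

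**Conclusion.** The gap in the wording is real. Following the text as written admits subjects whose Phase 1 Day 0 sCD14 and stool the plan would itself regard as unwashed had the course begun a few days later. The exposed quantities are the Phase 1 baseline, the difference of differences for primary and secondary markers, the Day 7 and Day 14 visits of Phase 1, and the baseline stool. The effect is mainly added noise or chance imbalance.

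A reader might infer that the primary result is biased or the trial underpowered; neither follows. About 4 weeks have passed by Phase 1 Day 28 (25 days at the extreme of the visit window for a course that ran up to Day 0), and the power calculation is untouched.

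The conclusion rests on two assumptions: that other antibiotics disturb flora for a period comparable to the plan's 4 weeks, and that few screenees have had a recent short course. The documents give no figure for the second, so the number affected is unknown, though probably small. This is a cheap improvement of low severity.

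**What to change.** Reconcile 3.4 with 4.7. State in the eligibility criteria that a course completed shortly before screening, or continuing into it, falls under the same antibiotic-free interval before Day 0 that 4.7 already applies to courses started in screening. The sponsor should confirm the interval. Add a question on recent antibiotic use, with the date of the last dose, to the medical history already planned at Screen 2.

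The cost is one eligibility line, one history item and the deferral of a few subjects by some weeks. If the 4 weeks in 4.7 are kept, a subject whose last dose was the day before Screen 1 reaches Day 0 no earlier than 28 − 1 = 27 days after Screen 1. That is within the 65 days allowed between screens and the 70 days allowed for safety laboratory tests before randomization. A course that ends later in screening counts from its own end, and an occasional subject may then need repeat laboratory tests.

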### **3.5 Co-enrollment Guidelines**

Co-enrollment in other trials is restricted, other than for observational studies, or those that allow for co-enrollment.. Study staff should ask subjects if they are participating in other studies and inform the site principal investigator/designee.

### **3.6 Justification for Exclusion of Pregnant and Breastfeeding Women and Children**

Pregnant women are excluded from this study because the effects of rifaximin on the developing human fetus are unknown with the potential for teratogenic or abortifacient effects. There is an unknown but potential risk for adverse events in nursing infants secondary to treatment of the mother with rifaximin, breastfeeding mothers will not be included in this study. Children will be excluded from this study as this study is unlikely to show any direct benefit to the child.

## **4 STUDY AGENT**

### **4.1 Disposition and Dispensation**

The study agent [rifaximin/placebo] will be distributed via the NIH Central Pharmacy (NIH PDS) according to standard pharmacy procedures. Both study drug and placebo will be formulated by the NIH PDS and will be supplied to the sites.

### **4.2 Formulation, Packaging, and Labeling**

Both placebo and drug will be identical in appearance. Commercial rifaximin 550 mg tablets are purchased by the Clinical Center Pharmacy Department. They are re-formulated into a light blue, opaque, size 0, hard gelatin capsule. Each capsule contains 183.3 mg rifaximin with microcrystalline cellulose and sodium starch glycolate as filler. A matching placebo capsule will be formulated as a light blue, opaque, size 0, hard gelatin capsule containing microcrystalline cellulose and sodium starch glycolate. Capsules also contain a Colorcon® aluminum lake blend of FD&C yellow #5/tartrazine, FD&C #6/sunset yellow, and FD&C 40 allura red. They will be packaged and labeled with the study number, and will have a space for the subjects initials and randomization number to be entered. Each bottle will be individually labeled with the subject ID number, dosing instructions, recommended storage conditions, the name and address of the manufacturer, and the subject's randomization number.

### **4.3 Study Products**

#### **Drug:**

Description- Rifaximin capsules for oral administration

Dosing and Administration- 550 mg will consist of three capsules to be taken twice a day.

Route of Administration- Oral

Duration of Therapy- 28 days (56 doses)

#### **Control Product:**

Description: Placebo will be identical in appearance to rifaximin

Dosing and Administration: three placebo capsules twice a day

Route of Administration- Oral

Duration of Therapy- 28 days (56 doses)

Storage and Stability- Both rifaximin and placebo can be stored between 59-86 degrees Fahrenheit (i.e., room temperature)

#### **4.4 Study Product Accountability Procedures**

Study product dispensing and shipping records will be maintained centrally by the NIH PDS including shipping records. The University of Pittsburgh and Walter Reed National Military Medical Center (WRNMMC) will maintain study product dispensing and accountability records. Study products will be dispensed to the sites by NIH PDS and remaining study product will be returned to the NIH PDS at the conclusion of the study. Subjects will obtain study product per the study visit schedule.

#### **4.5 Assessment of Subject Compliance with Study Agent/Intervention(s)**

Subjects will be asked to bring their bottle of study product to each study visit. Pill counts will be performed and recorded at each visit to monitor adherence to the protocol, and subjects will be asked about their adherence to study drug.

#### **4.6 Concomitant Medications and Procedures**

All concomitant medications taken during study participation will be captured at every study visit. Medications to be reported are concomitant prescription medications, over-the-counter medications and non-prescription medications including dietary and herbal supplements. This will be assessed at enrollment and updated periodically at study visits. Prescription medication is a medication that can be prescribed only by a properly authorized/licensed clinician.

#### **4.7 Prohibited Medications and Procedures**

Treatment with immunomodulating agents including systemic steroids in the 3 months prior to screening will not be permitted as these drugs have the potential to affect the primary outcome of the study. Subjects on topical steroids will not be excluded. Concurrent statin use will be permitted if subjects have been receiving stable doses of statins for 6 or more months. The use of concurrent antibiotics/oral steroids will not be permitted while on study drug. If a subject needs to initiate antibiotic/oral steroid therapy while he/she is on the study drug, the patient will discontinue the study drug, complete the course of antibiotics/oral steroids, undergo a 4 week washout and will re-initiate the study drug starting from Day 0 of the treatment phase. Subjects initiating antibiotics/oral steroids during the screening or washout phases of the study will have these phases extended by 4 weeks after completion of the antibiotic/oral steroid course. Routine vaccinations (i.e., influenza) may be administered during the screening process or washout phase. Subjects receiving routine vaccinations during the washout phase will have their washout extended to 6 weeks.

### **5 STUDY SCHEDULE**

#### **5.1 Screening Visits 1 and 2**

After signing the study informed consent, subjects will undergo 2 screening visits.

At the first screening visit subjects will undergo HIV testing (screening/confirmation if prior documentation of HIV status is unavailable)

Subjects found to be eligible for the study after the first screening visit will undergo the following procedures during the second screening visit:

- Complete medical history and physical examination
- Blood draw for
  - Immunophenotyping to include a CD4+ count and cellular markers of activation (including CD38+ and HLA-DR co-expression on both CD4+ and CD8+ cells)
  - Markers of bacterial translocation (including LPS, bacterial 16SrDNA or bacterial RNA and sCD14)
  - Liver function tests (including bilirubin, alkaline phosphatase (SAP), AST and ALT)
  - Renal function tests (including blood urea nitrogen (BUN), creatinine, electrolytes)
  - Complete blood count with differential (including platelets)
  - Coagulation parameters (including prothrombin time (PT) and international normalized ratio [INR])
  - Hepatitis B panel (including hepatitis B surface antigen)
  - Hepatitis C RNA assay
  - Single copy assay

Screening visits 1 and 2 must be separated by 48 hours and be no more than 65 days apart.

Screening visit 2 must be completed prior to randomization. Standard safety laboratory testing (blood counts, renal and liver function tests, coagulation studies, Hepatitis B and C panels) will be completed at the enrolling site. To minimize variability, all remaining laboratory testing will be done centrally at the NIH laboratory [Leidos Biomedical Research, Inc.].

